4.1.7 Assessment of Expectedness

Where reported, SAEs will be assessed for having a possible causal relationship with the intervention or its associated procedures. Where a causal relationship is established an evaluation of expectedness will be made by the CI or their delegate, using the list below. The following are SAEs that are expected as a result of the intervention and its associated procedures:

Those related in general to surgery and anaesthetic:

- Injury to teeth, mouth, or throat during anaesthetic.
- Chest infection.
- Nerve or vessel injury due to local anaesthetic (i.e., local blocks or spinal anaesthetic).
- Spinal haematoma.
- Stroke or Cardiac Event.
- Death.

Those related to the operation itself or physiotherapy:

- Exacerbation/persistence of knee pain or instability beyond what is considered
 normal by the treating clinical team. As this outcome will be captured in Patient
 Reported Outcome Measures (PROMs) throughout the study, only medical or
 surgical interventions for persistent knee pain need to be reported.
- Restriction of range of motion, including need for manipulation under anaesthetic,
 arthroscopic or open procedures to relieve stiffness.
- Infection.
- Wound healing problems.
- Fracture, ligament or tendon damage or rupture.

- Revision surgery or other corrective surgery.
- Irritation from metalwork or surgery to remove metalwork.
- Thrombosis (deep vein thrombosis, pulmonary embolus, cerebral infarct).
- Damage to nerves or vessels.
- Persistent muscle soreness or muscle injury.
- Bruising.
- Swelling.
- Skin damage (for example, from bracing).
- Exercise-related fatigue.

Treatments of expected events listed above (such as surgery for infection or wound problems) are also expected events.

If the SAE is not listed above and is considered to have at least a possible causal relationship to the intervention, the event would therefore be classified as unexpected and will be reported to the REC within 15 days.

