1.6 Assessment and management of risk

These intervention packages are both standard interventions, used in the NHS at present. Risks will be no different from those that occur in normal practice. Inevitably, there is some additional risk related to the surgery group over the Personalised Knee Therapy group as any operation has inherent risks, and the wait for surgery may be longer, but not beyond what is normal for NHS practice. A risk assessment will be performed according to Warwick SOPs and a monitoring plan developed depending on the risks identified. Risks specific to the trial include risks of data breaches, incorrect allocation, or failure to recognise safety concerns. These risks will all be carefully managed by following Warwick SOPs and careful adherence to the principles of Good Clinical Practice (GCP).

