4.2 Responsibilities

Principal Investigator (PI) (or delegated clinician):

- Checking for AEs when participants attend for treatment/follow-up.
- Using medical judgement in assigning seriousness and causality.
- Ensuring that all SAEs (according to the trial criteria) are recorded and reported to
 the Sponsor within 24 hours of becoming aware of the event and provide further
 follow-up information as soon as available. Ensuring that SAEs are chased with
 Sponsor if a record of receipt is not received within two working days of initial
 reporting.
- Ensuring that AEs are recorded and sent to the central trial team at WCTU in line with the requirements of the protocol and Warwick SOPs.

Chief Investigator (CI) / delegate or independent clinical reviewer:

- Clinical oversight of the safety of patients participating in the trial, including an ongoing review of the risk/benefit.
- Using medical judgement in assigning causality and expectedness.

- Timely review of all related and unexpected SAEs
- Review of specific SAEs in accordance with the trial risk assessment and protocol as detailed in the Trial Monitoring Plan (TMP).
- Production and submission of annual reports to the relevant REC.
- Monthly review of accumulated AEs/SAEs at TMG meetings.

Sponsor (University of Warwick):

- Central data collection and verification of AEs, and SAEs, according to the trial protocol.
- Reporting safety information to the CI, delegate, or independent clinical reviewer for the ongoing assessment of the risk/benefit according to the TMP.
- Reporting safety information to the independent oversight committees identified for the trial (Data Monitoring Committee (DMC) and/or Trial Steering Committee (TSC)) according to the TMP.
- Expedited reporting of related and unexpected SAEs to the REC within required timelines.
- Notifying Investigators of related and unexpected SAEs that occur within the trial.

Trial Steering Committee (TSC):

• In accordance with the TSC Charter, periodically reviewing safety data (without reference to allocation) and liaising with the DMC regarding safety issues.

Data Monitoring Committee (DMC):

• In accordance with the DMC Charter, periodically reviewing safety data, overall and by allocation group to determine patterns and trends of events, or to identify safety issues, which would not be apparent on an individual case basis.

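### Section 4.1.7 puts operative and physiotherapy harms in one expected-SAE block, so a related infection, thrombosis or nerve or vessel injury in a never-operated PKT participant counts as expected and misses the 15-day REC report

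*Protocol*

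**What the plan says.** Protocol section 4.1.7 sets out how expectedness is decided: "Where a causal relationship is established an evaluation of expectedness will be made by the CI or their delegate, using the list below". The list has two blocks. The first, "Those related in general to surgery and anaesthetic", has six entries. The second, "Those related to the operation itself or physiotherapy", has 14. It holds infection, wound healing problems, revision surgery, metalwork irritation, "Thrombosis (deep vein thrombosis, pulmonary embolus, cerebral infarct") and "Damage to nerves or vessels" next to muscle soreness, bracing-related skin damage and exercise fatigue. Treatment of any listed event is also expected.

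The section closes with the test for an unexpected event: "If the SAE is not listed above and is considered to have at least a possible causal relationship to the intervention", it is unexpected and goes to the REC within 15 days. Section 4.1.4 gives the same 15-day route for related and unexpected events. Section 4.2 lists among the Sponsor's duties "Notifying Investigators of related and unexpected SAEs that occur within the trial".

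Section 4.2 also gives the CI, a delegate or an independent clinical reviewer the task of using medical judgement on causality and expectedness. Section 1.6 states that the two arms differ in risk: "Inevitably, there is some additional risk related to the surgery group over the Personalised Knee Therapy group as any operation has inherent risks".

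**The concern.** Expectedness decides which related SAEs are expedited. It works as intended only if an event is compared with what is anticipated from the treatment the person actually had. In the second block the heading names physiotherapy, the entries include harms typical of an operation, and nothing says which entries apply to whom.

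If a serious event of one of these kinds were attributed to PKT in someone never operated on, the written rule would treat it as anticipated because the same category is listed for surgery. The REC and the other investigators would then not hear of it by the expedited route, even if the clinical group regarded it as unforeseen for an exercise-based programme.

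**Working it through.** No published figure has to be reproduced. The check follows one event through the rules and then asks how many entries matter.

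**Tracing the rule.** Take a PKT participant who has had no operation or anaesthetic and has a serious thrombosis or nerve injury.

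1. *Is it reportable?* Yes, if it relates to the treated knee or the trial treatment (4.1.1, 4.1.3). It is reported within 24 hours (4.1.4, 4.2).
2. *Is it related?* Suppose the site's delegate or the Sponsor's delegate finds a possible causal link with PKT. Under 4.1.6 either finding is enough to require an expectedness assessment.
3. *Is it expected?* Section 4.1.7 says to use the list. Both events stand under the heading that names physiotherapy, so they are listed and the closing test is not met. The event is expected.
4. *What follows?* The 15-day REC report (4.1.4, 4.1.7) and the notification of investigators (4.2) apply only to related and unexpected events. Neither is triggered.
5. *What still happens?* The Sponsor has the report, the CI or delegate has assessed the event, accumulated SAEs are reviewed monthly at the TMG, and the DMC periodically reviews safety data by allocation group (4.2).

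**How many entries matter.** The list has 6 + 14 = 20 entries. The first six stand under a heading limited to surgery and anaesthetic, so on a fair reading they are not expected effects of PKT alone. The 14 shared entries can be sorted as follows. The sorting is mine, for scale only; the protocol does not sort them.

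| Group | Entries | Number |
|---|---|---|
| In the main presuppose an operation, so listing them hides little in an unoperated knee | wound healing problems; revision or corrective surgery; metalwork | 3 |
| Readily fit physiotherapy | worse or persistent pain or instability; restricted motion; muscle soreness or injury; bruising; swelling; skin damage; fatigue | 7 |
| Arguable either way | fracture, ligament or tendon damage | 1 |
| Can occur without an operation and are not assigned to either treatment | infection; thrombosis; nerve or vessel damage | 3 |

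3 + 7 + 1 + 3 = 14. The point therefore turns on about three entries, or four with fracture and rupture.

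**Who is exposed.** With 276 participants randomised 1:1, about 276 / 2 = 138 are allocated to PKT. Some of them will later have surgery, which sections 1.2.1 and 2.7.2 accept. The protocol gives no rate for these events under physiotherapy, so the number misrouted cannot be estimated.

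**The case against.** The strongest reply is that little would be lost. Every reportable SAE reaches the Sponsor within 24 hours whether or not it is expected. Causality has two independent assessments. The CI or delegate must look at each related SAE in order to judge expectedness, and the DMC reviews by allocation group to find patterns of this kind. All of that stands. It limits the consequence to the 15-day REC report and the notification of investigators.

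Second, section 4.2 provides for medical judgement on expectedness, so an assessor might depart from the list. This stands in part. Section 4.1.7 ties the evaluation to the list and ends with a mechanical test. Two assessors could classify the same event differently, and each could cite the protocol.

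Third, the authors put these entries under a heading that names physiotherapy, perhaps on purpose. That is possible, and which harms are foreseeable with PKT is a clinical question. But the same block contains metalwork irritation and revision surgery, so its entries cannot all have been meant for both treatments, and the text does not show which were.

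Four stronger readings are tempting and are not supported:
- That all 20 entries are expected for PKT. The heading of the first block limits its six entries to surgery and anaesthetic.
- That CI review is missed. Section 4.2 does reserve one line of timely review for related and unexpected SAEs, but the CI or delegate will already have seen the event, and SAEs are reviewed monthly.
- That the PKT arm can never generate an expedited report. A related SAE outside the list still would, and judgement may allow others.
- That the relative risk of 9.10 in section 1.2.2 proves the point. It concerns how often adverse events occur, not which kinds are foreseeable, and the protocol rates that evidence as very low quality.

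**Conclusion.** The point holds in a narrow form. Read as written, section 4.1.7 classes a related infection, thrombosis or nerve or vessel injury in a never-operated PKT participant as expected, and so withholds the 15-day REC report and the notification of investigators.

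This rests on two assumptions: that assessors apply the list literally, and that at least one of these entries would not be judged an expected harm of physiotherapy alone. The first is the plain reading of 4.1.7. The second is for the trial's clinical group to settle.

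This is a minor safety-reporting correction. The events are probably rare and other layers of review remain. No analysis described in section 6 uses expectedness, so a reader should not infer any effect on the efficacy results. It is still worth making, because the protocol states a rule that can send a serious event down the wrong route.

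**What to change.** Amend section 4.1.7 and the SAE assessment form to:

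- state expectedness in two lists, keyed to treatment received before the event whatever the allocation: (i) after any knee operation or anaesthetic; (ii) physiotherapy or PKT only;
- say that a related SAE in an unoperated participant is judged only against list (ii), and that anything not on it is unexpected and follows the 15-day route;
- reconcile the medical-judgement wording in 4.2 with 4.1.7 by saying whether an assessor may depart from the list and, if so, that the reason is recorded.

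Treatment received is a better key than allocation because PKT participants may later have surgery and some allocated to surgery may never have it. The clinical group decides which entries belong on which list; this review proposes none.

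The cost is a short amendment and a form change. The downside is possibly a few more expedited reports over the trial.

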4.2 Responsibilities

Principal Investigator (PI) (or delegated clinician):

- Checking for AEs when participants attend for treatment/follow-up.
- Using medical judgement in assigning seriousness and causality.
- Ensuring that all SAEs (according to the trial criteria) are recorded and reported to
 the Sponsor within 24 hours of becoming aware of the event and provide further
 follow-up information as soon as available. Ensuring that SAEs are chased with
 Sponsor if a record of receipt is not received within two working days of initial
 reporting.
- Ensuring that AEs are recorded and sent to the central trial team at WCTU in line with the requirements of the protocol and Warwick SOPs.

Chief Investigator (CI) / delegate or independent clinical reviewer:

- Clinical oversight of the safety of patients participating in the trial, including an ongoing review of the risk/benefit.
- Using medical judgement in assigning causality and expectedness.

- Timely review of all related and unexpected SAEs
- Review of specific SAEs in accordance with the trial risk assessment and protocol as detailed in the Trial Monitoring Plan (TMP).
- Production and submission of annual reports to the relevant REC.
- Monthly review of accumulated AEs/SAEs at TMG meetings.

Sponsor (University of Warwick):

- Central data collection and verification of AEs, and SAEs, according to the trial protocol.
- Reporting safety information to the CI, delegate, or independent clinical reviewer for the ongoing assessment of the risk/benefit according to the TMP.
- Reporting safety information to the independent oversight committees identified for the trial (Data Monitoring Committee (DMC) and/or Trial Steering Committee (TSC)) according to the TMP.
- Expedited reporting of related and unexpected SAEs to the REC within required timelines.
- Notifying Investigators of related and unexpected SAEs that occur within the trial.

Trial Steering Committee (TSC):

• In accordance with the TSC Charter, periodically reviewing safety data (without reference to allocation) and liaising with the DMC regarding safety issues.

Data Monitoring Committee (DMC):

• In accordance with the DMC Charter, periodically reviewing safety data, overall and by allocation group to determine patterns and trends of events, or to identify safety issues, which would not be apparent on an individual case basis.

4.3 Notification of deaths

All deaths where there may be a relationship between the trial interventions or the condition being studied (in this case, any knee condition, or an event related to the anaesthetic, surgery, hospital admission, physiotherapy) will be reported by the CI to the sponsor. This report will be as soon as the CI becomes aware of the event. Reporting processes to other organisations (REC and the manufacturer) will be as documented above."

4.4 Reporting urgent safety measures

If any urgent safety measures are taken the CI/Sponsor shall immediately and in any event no later than three days from the date the measures are taken, give written notice to the relevant REC of the measures taken and the circumstances giving rise to those measures.

5 DATA MANAGEMENT

All processes related to data management will be detailed in the Data Management Plan (DMP).

Personal data collected during the trial will be handled and stored in accordance with the UK General Data Protection Regulation (UK GDPR).

Personal identifying information will be held at WCTU for follow-up purposes. We will also request permission from participants to retain contact details to send a summary of the trial at the end of the trial and for long-term follow-up if funding is secured. Handling of personal data will be clearly documented in the patient information sheet and consent obtained.

Disclosure of confidential information will only be considered if there is an issue which may jeopardise the safety of the participant or another person, according to Warwick SOPs (SOP 15 part 1) and the UK or local regulatory framework. There is no reason to expect this situation to occur in this trial more than any other. Data requests from participants would be handled following SOPs (SOP 35).

5.1 Data collection and management

Case Report Forms (CRFs) will be developed to collect all required trial data.

The CRFs will be developed by the TM in consultation with the CI, Trial Statistician, Health Economist, and other relevant members of the trial team. They will be produced in English initially, although translation requirements will be reviewed if screening data reveals that language barriers are affecting participation and a predominant language, or languages, can be identified.

Participants will be given the option to use an App or website page for follow-up data collection when they consent to join the trial. The use of digital means for data collection, such as an app, was preferred to paper forms by all patients who we have discussed this with. This should improve the response rate and participant experience in this trial. However, paper forms will still be used for those who prefer them, or for non-responders. These can be returned by post or scanned and returned electronically. We will also give the participants the option of telephone follow-up.

We have a quote for delivery of a study app from a UK company with an established digital platform for data collection in orthopaedic patients (Future Health Works; myrecovery.ai). We have worked with them successfully to develop apps for multiple studies in our unit using the same platform, (ARTISAN, NIHR HTA; RACER, NIHR HTA; METRO NIHR DRF). The company already have permissions to use the measures (including EQ-5D-5L), they have completed independent data security checks, and have full approval from the University of Warwick's Information Technology department for the platform to be used for data collection in clinical trials.

Participants may be invited for clinical follow-up at 12 and 18-months. If the central team at Warwick CTU is having or anticipates (based on previous follow-ups) difficulties collecting the follow-up data at 12 and/or 18 months via app, electronic questionnaire, post or telephone from an individual, the central team will contact the site research teams to ask if they can invite the participant in to site for a clinical follow up to collect this data. This clinical follow up is normal care in some centres and additional in others, therefore, we have costed for these visits in the SoECAT. There may also be additional costs for translators.

All participants will be given a £10 gift voucher at the six, 12 and 18-month follow-up timepoints, which would remunerate any travel costs for this. In the pilot, a clinical follow-up helped support collection of outcome data, especially for people who lack confidence in written English where a member of the site research team can support them in completing questionnaires. Additionally, this strengthens the inclusivity of the trial. A pen and teabag will be sent with postal questionnaires at the 24-month timepoint.

Participants will be reminded to complete questionnaires via text messaging, phone, post or by email to improve response rate.(65, 66) Our PPI feedback was positive about this as a way of reminding people. As is typical for our unit, we will take multiple contact details, including next of kin, (which will be stored securely in the trial database/MyRecovery App, to ensure a high response rate. Participants will only provide next of kin details where they have prior permission to do so. Where people do not respond (with prior consent), we will write to their GP to request information on potential complications or re-operations or from routine datasets, to ensure we do not miss critical safety data.

5.2 Database

The database will be developed by the Programming Team at WCTU and a full specification (e.g., database variables, validation checks, screens) will be agreed between the programmer and appropriate trial staff.

5.3 Data storage

All essential documentation and trial records will be stored at WCTU in conformance with the applicable regulatory requirements and access to stored information (paper and electronic) will be restricted to authorised personnel. All data will be stored in a designated storage facility within hospital sites taking part in the trial, and/or WCTU. Electronic data will be stored on password protected university computers in a restricted access building. Data (including personal data) will be removed from the MyRecovery records/Qualtrics once we have completed the final follow up of the final participant.

5.4 Data access and quality assurance

All data collected will be de-identified after the collection of the baseline demographic data for each participant, except where this is not possible such as contact details for follow-up, in which case it will be kept separately.

Confidentiality will be strictly maintained, and names or addresses will not be disclosed to anyone other than the staff involved in trial follow-up. Participants will be identified by ID number, initials, and age only where necessary. Any identifiable participant data on paper will be held separately in a locked filing cabinet and coded with the trial number to tag identifiable data to the outcome data.

Direct access to source data/documents will be available for trial-related monitoring or audit by WCTU, or REC.

The PI must arrange for retention of trial records on site in accordance with GCP and local Trust's policies.

5.5 Data shared with third parties

De-identified data that underlie the results reported in the trial will be available for non-commercial use, up to one year after publication of the primary outcome trial findings, or from metadata stored in a university repository up to 10 years without investigator support.

A data dictionary will be produced. To access trial data, third parties must complete a data-sharing agreement with the sponsors, have an ethically approved protocol in place for use of the data, and agree the approved protocol with the REPPORT TMG and WCTU data sharing committee. Data may be used for commercial purposes, according to the conditions above, but will need specific agreements in place prior to access being agreed, this may include a license fee. Analyses may include individual patient data meta-analyses or other purposes as agreed with the REPPORT TMG.

Available data will include (but is not exclusive to) de-identified individual participant data that underlies the results reported in trial publications, the trial protocol, statistical analysis plan, master copy of the informed consent sheets and scripts or files used to conduct trial analyses.

After one year following the publication of the final report, the data will be stored in an appropriate repository, it may still be available according to the conditions laid out above but may not receive investigator support.

